11.2.1 Infusion Related Reactions (IRR)

IRRs are those TEAEs which occur during the infusion or shortly after the completion of the infusion and their causality is assessed as definitely, probably, or possibly related.

Injection site reactions with SOC and PT listed in Table 3 are not considered IRR and should not be considered for the IRR analysis.

Two time-frames will be considered for the IRR analysis: during the infusions or within 2 hours after its completion (IRR-2H) or within 24 hours after its completion (IRR-24H). Classification rules for assignment of TEAEs to occur within the time frame are provided below. All IRR tables will be done on IRR-2H. Selected tables will be repeated for IRR-24H, as described below.

Table 3: Injection Site Reaction SOC and PT

MedDRA SOC	MedDRA Preferred Term
General disorders and administration site	Infusion site discomfort
conditions	Injection site discomfort
	Infusion site pain
	Injection site pain
	Infusion site hematoma
	Injection site hematoma
	Injection site extravasation
	Infusion site extravasation
Injury poisoning and procedural complications	Contusion
	Procedural site reaction
	Procedural pain
Vascular disorders	Vein rupture
	Poor venous access

The number and percentage of patients with at least one IRR and the number of IRRs will be reported by treatment group and overall, in an overview table with the following parameters: Any IRR; Mild or moderate IRR; Severe IRR; Serious IRR; IRR leading to withdrawal; IRR leading to death. For selected summary tables, the number of IRR will be shown together with the rate per 100 infusions defined as number of IRR X 100 / Number of Infusions.

This analysis will be repeated for IRR-24H.

This analysis will be repeated for the following sub-groups: ADA status, gender, FD classification and region.

The analysis will be also by the location of administration (Home or Site), and repeated for IRR-24H.

IRR summary tables by SOC and PT will present the number and percentage of patients with at least one IRR and the number of IRRs. The tables for the IRRs will be presented overall, by severity and by seriousness. The tables by SOC and PT will be repeated for IRR-24H.

In summary tables by SOC and PT, SOC will be sorted alphabetically. Within SOC, PT will be sorted in a decreasing order of PRX-102 frequency.

IRR-2H and IRR-24H will be listed.

11.2.2 TEAE Occurring During the Infusion or Within 2 Hours After the Infusion

To determine whether a TEAE occurred within this time frame, information collected in two eCRF pages will be considered: AE form (fields of onset date and time) and Drug Administration form (fields of administration date; start and end times; question 1 "Did the patient experience an AE during or after the infusion?" and the sub-questions in case the answer is Yes. The sub-questions are 1a: "During the infusion", 1b: "Within 2 hours after the infusion" or 1c: "Up to 24 hours after the infusion"). Events which meet one of the following criteria will be considered to occur during infusion or within 2 hours after the infusion:

- Date and time for both TEAE and infusion are complete, and the onset of the TEAE is during the infusion or within 2 hours from its completion (stop time), regardless of the answer to question 1 above;
- The answer to question 1 above is Yes, and the options selected are either 1a or 1b, and the AE is linked to the drug administration form.

All other events will not be classified into this time category.

11.2.3 TEAE Occurring During the Infusion or Within 24 Hours After the Infusion

The algorithm is similar to above with a slight modification to the two conditions, as below:

- Date and time for both TEAE and infusion are complete, and the onset of the TEAE is during the infusion or up to 24 hours from its completion (stop time), regardless of the answer to question 1 above;
- The answer to question 1 above is Yes (regardless of selection of 1a, 1b or 1c) and the AE is linked to the drug administration form.

All other events will not be classified into this time category.

11.3 Vital Signs

The vital signs (systolic and diastolic blood pressure, pulse rate, body temperature, and respiratory rate) will be summarized by treatment arm at each visit. Within each visit, vital signs and change from pre-dose will be summarized for pre-dose, and nominal times of 30 minutes, 1h, 2h, 3h, 4h, 5h and 6h from start of infusion and in addition the end of observation assessment will be also presented.

In case that vital signs are taken at additional time points, or that the nominal time points are not as above, then the measurements will only be listed (e.g., if measurements are taken at 15, 30, 45, 75, 105 minutes then the measurements at 15, 45, 75 and 105 will only be listed).

11.4 Physical Examination

The number and percentage of patients with respect to physical examination results (normal / abnormal / not done) will be summarized by body system (as described in eCRF) at each visit by treatment group.

11.5 Clinical Laboratory Test Results

The following laboratory test results will be summarized by treatment arm at each visit. Continuous measures will include the change from Baseline:

- 1. Hematology: Hemoglobin (g/dL), Platelets (/mm3), Total white blood cell count (/uL)
- 2. Coagulation Profile: Partial thromboplastin time (PTT; sec), Prothrombin time (PrT; sec)
- 3. Vitamin D: D2 (pg/mL), D3 (pg/mL), 1,25-Dihydroxyvitamin D (pg/mL)
- 4. Urinalysis: Dipstick for presence of blood, Dipstick for presence of glucose, Dipstick for presence of Protein.
- 5. Biochemistry: Alanine transaminase (U/L), Albumin (g/dL), Alkaline phosphatase (U/L), Aspartate transaminase (U/L), Bilirubin (total) (mg/dL), Blood urea nitrogen (mg/dL), Calcium (mg/dL), Creatinine (mg/dL), Creatine phosphokinase (U/L), Cystatin c (mg/L), Gammaglutamyl transferase (U/L), Glucose (mg/dL), Lactate dehydrogenase (U/L), Phosphate (inorganic) (mg/dL), Potassium (mEq/L), Sodium (mEq/L), Total protein (g/dL) and Uric acid (mg/dL).

Note: serum creatinine can be recorded in two units, μ mol/L and mg/dL. In calculation of eGFR or summary of creatinine, the value in μ mol/L needs to be converted to mg/dL using the following conversion formula: 1 mg/dL = (1/88.4) μ mol/L.

Note: Serum creatinine is present in two laboratory test categories in the Study Data Tabulation Model (SDTM) (CHEMISTRY and ENZYMATE). When results from the same sample are entered at both laboratory test category, then the value is identical. In such cases, only one of them will be used in the analysis.

In case that blood sample is taken twice at the same visit, only the results of the first blood sample (based on the time the blood sample was taken) will be used in the analyses, but both will be listed.

All collected laboratory results will be listed (also parameters that are not tabulated).

Descriptive statistics for parameters for which there are test results below the level of detection and reported as '<', will not include the change from baseline analysis. For these parameters, the analysis of actual values at the visit will be based only on the values for which the true value was observed, and the summary will indicate the number of observations that were below the limit of detection. In the listings, these observations will be presented with the '<' sign.

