6.2.1 Inclusion Criteria

The subjects must fulfil the following inclusion criteria:

1. Symptomatic adult Fabry disease patients, age 18-60 years
2. Males:
plasma and/or leucocyte alpha galactosidase activity (by activity assay) less than 30% mean normal levels and one or more of the characteristic features of Fabry disease
 - i. neuropathic pain
 - ii. cornea verticillata
 - iii. clustered angiokeratoma
3. Females:
 - a. historical genetic test results consistent with Fabry pathogenic mutation One or more of the described characteristic features of Fabry disease:
 - i. neuropathic pain,
 - ii. cornea verticillata,
 - iii. clustered angiokeratoma
 - b. or in the case of novel mutations a first degree male family member with Fabry disease with the same mutation, and one or more of the characteristic features of Fabry disease
 - i. neuropathic pain,
 - ii. cornea verticillata,
 - iii. clustered angiokeratoma
4. Screening eGFR by CKD-EPI equation 40 to 120 mL/min/1.73 m²
5. Linear negative slope of eGFR of ≥ 2 mL/min/1.73 m²/year based on at least 3 serum creatinine values over approximately one year (range of 9 to 18 months including the value obtained at the screening visit)
6. Treatment with a dose of 1 mg/kg agalsidase beta per infusion every 2 weeks for at least one year and at least 80% of 13 (10.4) mg/kg total dose over the last 6 months
7. Female patients and male patients whose co-partners are of child-bearing potential agree to use a medically accepted method of contraception, not including the rhythm method.

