10.3 Analysis

10.3.1 Primary Efficacy Analysis

eGFR is calculated from the serum creatinine according to the CKD-EPI formula:

$$\text{eGFR (ml/min/1.73 m}^2\text{)} = 141 \times \min(\text{Scr}/\kappa, 1)^\alpha \times \max(\text{Scr}/\kappa, 1)^{-1.209} \times 0.993^{\text{Age}} \times 1.018 \text{ [if female]} * 1.159 \text{ [if black]}$$

Scr = serum creatinine; $\kappa = 0.7$ for females and 0.9 for males; $\alpha = -0.329$ for females and -0.411 for males, min indicates the minimum of Scr/κ or 1 , and max indicates the maximum of Scr/κ or 1 .

The primary efficacy analysis compares the estimated annualized slope of the glomerular filtration rate (eGFR) between the PRX-102 group and the agalsidase beta (Control) group over 2 years. A longitudinal mixed model will be used to estimate the eGFR slope in the two groups by examining time and group as fixed effects and patient as a random effect in the model. The time by group interaction will be examined to determine if there is evidence that the eGFR slope rates are different between groups. Since the primary comparison is a test of superiority at 24-months, this interaction is expected to be statistically significant. If the interaction test is significant this would indicate that the eGFR slopes are statistically significantly different and depending on the direction of the difference it would indicate that the PRX-102 group is superior (or inferior) to the Control group for this measure. Using this longitudinal mixed model, the assumption of whether the change in eGFR is linear over time will be examined. Specifically, residual plots will be estimated from the model to determine whether there is evidence of nonlinearity over time. If there is evidence of non-linearity, transformations of the primary outcome will be considered (*i.e.*, log transformation, etc.). If a transformation is needed, the model will be re-fit with the transformation and assessments of linearity will be made again. If a transformation is used and it provides evidence of linearity, slopes will be estimated on the transformed scale with corresponding 95% confidence intervals for the difference in slopes between groups.

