1. INTRODUCTION

This statistical analysis plan (SAP) contains detailed information on the definition of the analysis populations, derivation of variables, conventions of analysis scope, and statistical methodology for the analyses of efficacy and safety of pegunigalsidase alfa (also known as PRX-102) and agalsidase beta administered by intravenous (IV) infusion based on data collected per protocol PB-102-F20, a Phase 3 study sponsored by Protalix Ltd. Should the SAP and the protocol be inconsistent with respect to the planned analyses, the language of the SAP is governing.

The pharmacokinetic (PK) analysis is not within the scope of this SAP and is detailed in a standalone PK analysis plan.

A pre-planned interim analysis occurred when the last patient completed the 12-month visit to support a Marketing Authorization Application (MAA) submission to the European Medicines Agency (EMA). The final analysis will occur when the last patient completes the 24-month visit and will support a biologics license application (BLA) re-submission to the FDA.

The SAP that was signed on April 15th, 2021 prior to Data Base Lock (DBL) and unblinding for the interim analysis, included non-inferiority of PRX-102 compared to agalsidase beta for the interim analysis and superiority of PRX-102 compared to agalsidase beta for the final analysis. However, following the conversion of agalsidase beta to a full approval in March 2021, it was agreed with the FDA (End-of-Review Meeting, Sep 9th, 2021) that it is not necessary anymore to demonstrate superiority over agalsidase beta. A Type C meeting to reach agreement with the FDA on the proposed primary model to assess non-inferiority took place in January 21, 2022 and the SAP reflects this discussion.

In addition, analysis that were conducted as post-hoc after the interim analysis are added to the SAP, as well as some other minor changes (all are documented). None of the analyses performed at the interim analysis will be removed but following a comment by FDA, covariates were changed.

As this SAP is now only for the final analysis, sections/paragraphs relating to the interim analysis were deleted and/or updated to include only the final analysis.

In light of the unplanned conversion of agalsidase beta to a full approval and the change in regulatory requirements following that, some changes had to be made also to the unblinding plan.

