This section is laid out as follows: Section 9.1 discusses the derivation of the eGFR from serum creatinine; Section 9.2 provides technical details for the proposed two-stage with quantile regression model; Section 9.3 describes the planned sensitivity and supportive analysis, Section 9.4 describes the sensitivity analyses to account for missing data, Section 9.5 describes the sensitivity analysis for AKI episodes and Section 9.6 describes the planned sub-groups to be examined for the primary endpoint.

All analysis described in this section will be conducted on the ITT analysis set. In addition, some of the analysis will be conducted also on the PP analysis set as sensitivity analysis

9.1 eGFR Derivation

eGFR will be derived based on the value of the serum creatinine using the CKD-EPI formula and rounded to 2 decimal places:

```
eGFR (mL/min/1.73 m^2) = 141 × min(Scr/\kappa,1)\alpha × max(Scr/\kappa, 1)\alpha × 0.993Age × 1.018 [if female] × 1.159 [if black / African American],
```

where Scr is serum creatinine (mg/dL), κ is 0.7 for females and 0.9 for males, α is -0.329 for females and -0.411 for males, min indicates the minimum of Scr/ κ or 1, and max indicates the maximum of Scr/ κ or 1. Age is the actual age when the patient's serum creatinine is collected.

Results of the serum creatinine test at the screening visit appear twice in the data-base: once as part of the data transferred from the central laboratory and once in the eCRF (once the site receives from the central laboratory, the value is entered into the eCRF to check the eligibility in terms of eGFR value and the eGFR slope). These two values should be identical. In the listings, by-visit tables of eGFR and slope calculations, the value entered into eCRF should be used anyway.

In case of two identical serum creatinine measurements taken at same date and time but assigned to two different visits, then it should be used only once and assigned to the visit that was performed on that date.

AKI Episodes are reported by the investigators as an AE. Serum creatinine measurements, if any, during an AKI episode will be excluded from the eGFR summary tables and any analysis related to eGFR. An AKI episode is defined between the start and the end date of the AKI AE. The number of eGFR measurements which are excluded from the analysis will be summarized by treatment arm.

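### SAP 11.5 prints the serum creatinine unit conversion upside down; the fault is minor, but the rule is tied to eGFR and takes one line to correct

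*SAP*

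**What the plan says.** SAP 9.1 derives the primary variable from creatinine: "eGFR will be derived based on the value of the serum creatinine using the CKD-EPI formula". The formula takes its input in mg/dL: "where Scr is serum creatinine (mg/dL").

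A note in SAP 11.5 says that "serum creatinine can be recorded in two units", µmol/L and mg/dL. For eGFR and for creatinine summaries, the µmol/L value "needs to be converted to mg/dL using the following conversion formula: 1 mg/dL = (1/88.4") µmol/L. Neither document contains another creatinine conversion rule.

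The resulting eGFR values are used in these places:
- SAP 8.3: the baseline eGFR slope, fitted to historical, screening and baseline creatinine plus any unscheduled values before baseline.
- SAP 7.4 and SAP 10.1: the subgroup split at −5 mL/min/1.73 m²/year, and the three kidney-disease groups with their therapeutic goals. Both use the eGFR slope before treatment.
- SAP 9.2: the first stage of the primary analysis, a straight line through all of a patient's eGFR values except those taken during an acute kidney injury episode.

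**The concern.** Read as an equation, the printed rule says that 1 mg/dL is about 0.0113 µmol/L. Anyone who substitutes with it would multiply a µmol/L value by 88.4 to reach mg/dL, when the value should be divided by 88.4.

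This is an instruction within the analysis plan and it is expressly linked to the calculation of eGFR. The SAP also takes precedence over the protocol for planned analyses: "Should the SAP and the protocol be inconsistent with respect to the planned analyses, the language of the SAP is governing". If the rule were coded as printed, any creatinine recorded in µmol/L would give a meaningless eGFR. A patient with values in both units would then have a badly distorted fitted slope.

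**Working it through.** **Inputs**
- Printed conversion: 1 mg/dL = (1/88.4) µmol/L (SAP 11.5).
- CKD-EPI formula with κ = 0.9 and α = −0.411 for men, and exponent −1.209 on the max term (Protocol 10.3.1 and Appendix 6).
- Molar mass of creatinine, 113.12 g/mol. This is a physical constant that the documents do not give, and it is used only to confirm the direction.

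**Step 1: direction of the conversion.** 1 mg/dL = 10 mg/L. Dividing by 113.12 g/mol gives 0.08840 mmol/L = 88.40 µmol/L. The number 88.4 is therefore right and the equation is inverted. The reading mg/dL value = µmol/L value × (1/88.4) does reproduce the correct factor.

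The documents' own scale agrees. Over the protocol's age range (18 to 60 years) and eligible eGFR range ("Screening eGFR by CKD-EPI equation 40 to 120" mL/min/1.73 m²), the CKD-EPI formula corresponds to creatinine of about 0.34 to 2.3 mg/dL. Multiplying by 88.4 gives about 30 to 203 µmol/L. The printed equation would instead give 0.34/88.4 ≈ 0.004 to 2.3/88.4 ≈ 0.026 µmol/L.

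**Step 2: size of the error.** Multiplying where one should divide gives a factor of 88.4 × 88.4 = 7,814.6.

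**Step 3: effect on one eGFR** (non-black man aged 45, creatinine 100 µmol/L; 0.993^45 = 0.7290)
- Correct: 100/88.4 = 1.131 mg/dL. eGFR = 141 × (1.131/0.9)^−1.209 × 0.7290 = 141 × 0.7585 × 0.7290 = 78.0.
- As printed: 100 × 88.4 = 8,840 mg/dL. eGFR = 141 × (8,840/0.9)^−1.209 × 0.7290 = 141 × 0.0000149 × 0.7290 = 0.0015. SAP 9.1 rounds eGFR to two decimals, so this becomes 0.00.

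For scale, the severity index in Protocol Appendix 5 places end-stage renal failure at creatinine above 3.5 mg/dL.

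**Step 4: effect on a fitted slope** (illustration only, because the documents give no count of µmol/L values). Assume 30 equally spaced readings over 2 years, eGFR 75 at the start and a true slope of −3.0. The sum of squared time deviations is 10.69.
- One misconverted first reading (75 becomes 0, one year before the mean time): −3.0 + 75 × 1/10.69 = +4.0.
- One misconverted last reading (69 becomes 0, one year after the mean time): −3.0 − 69 × 1/10.69 = −9.5.
- All readings misconverted: the slope is about −0.00006 before rounding, which is effectively zero.

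Values already recorded in mg/dL do not change.

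**The case against.** The strongest reply is that this is a fault of notation which nobody would carry into code. The sentence states the direction, µmol/L to mg/dL, and shows 1/88.4, which is the correct multiplier. Literal coding would yield eGFR values of 0.00 and could hardly be missed: the interim analysis has already been run on true treatment codes and reported (SAP 7.5 and 16.3), and a dry run and blinded data review come before the final lock (SAP 16.3.1).

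Exposure may also be small. On-study creatinine is evaluated by a central laboratory (SAP 16.4), and SAP 11.5 itself lists creatinine in mg/dL. The primary analysis compares median slopes, so one grossly wrong slope has limited influence on it.

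Most of this stands, and it is why the point is minor. It does not make the printed equation correct. SAP 11.5 expressly provides for µmol/L values, and the historical creatinine in the baseline slope is the likeliest place to find them. If only some of a patient's values were misconverted, the baseline slope could put that patient in the wrong kidney-disease group.

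**Conclusion.** The conversion in SAP 11.5 is inverted as printed. If coded literally, each value recorded in µmol/L would be wrong by a factor of about 7,815 and its eGFR would be near zero. Any effect on the results needs two things that the documents do not show: that some values are in µmol/L, and that the program multiplies by 88.4. The second is unlikely. The severity is minor.

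A reader might infer more than the documents support:
- **That the SAP uses a different CKD-EPI formula.** In the machine-read text of SAP 9.1, the max term appears to carry α where the protocol has "\max(\text{Scr}/\kappa, 1)^{-1.209"}. This rests on a single superscript. The SAP names CKD-EPI, gives the same κ and α as the protocol, and records no formula change in Section 13. The same text garbles repeated symbols elsewhere, for example the sampling times in footnote 3 of SAP Table 1. A PDF-reading fault is the probable explanation.
- **That the −3.0 margin becomes easier to meet.** The argument that slopes are quietly shrunk depends on that exponent and falls with it. Isolated conversion errors move a slope either way (step 4), and a patient misconverted throughout would show eGFR of 0.00 at every visit.
- **That eligibility was affected.** The screening slope was calculated within the EDC system (SAP 8.3), and enrolment ended in 2019 (SAP 6), before this SAP, which reflects a meeting in January 2022.
- **That the Per Protocol set is affected.** SAP 4.4 has violations reviewed at blinded meetings and does not say that eGFR is re-derived for that review.

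**What to change.** In SAP 11.5, replace the equation with Scr (mg/dL) = Scr (µmol/L) / 88.4, equivalently 1 mg/dL = 88.4 µmol/L. State that it applies to historical, screening and on-study values. Confirm before database lock that the program divides, and report how many creatinine values were recorded in µmol/L.

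The cost is one corrected line, one check of the code and one count. There is no downside.

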11.6 Electrocardiography (ECG)

Descriptive statistics for selected quantitative and qualitative ECG parameters will be summarized at each visit by treatment arm. For quantitative parameters, the change from baseline will be summarized. All parameters will be listed (note that for patients diagnosed with Atrial Fibrillation, all PR values are reported as 0 in the ECG report. This value should be considered as not accessible).

- 1. Quantitative ECG parameters: Mean Heart Rate
- 2. Qualitative ECG parameters: Rhythm Normal Sinus Rhythm (NSR), Conduction abnormalities, left ventricular hypertrophy, Supraventricular tachycardia, Premature atrial contraction, Atrial flutter, Atrial fibrillation, Premature ventricular contraction, Ventricular tachycardia, and any clinically abnormal findings (i.e., any abnormal condition as listed above). Note that ECG abnormalities and findings are reported as characteristic = Yes in the CRF,

except for Rhythm – Normal Sinus Rhythm (NSR), for which, an abnormality is reported as characteristic = No. For consistency purposes in the reporting, for this summary it has been reversed.

